8.2 Radiology Studies

8.2.1 Central Radiology Review for Response: Patients who respond (CR, PR) to therapy or have long term stable disease (SD) (≥ 6 cycles) on protocol therapy will be centrally reviewed. COG Operations Center will notify the Imaging Center of any patient requiring central review. The Imaging Center will then request that the treating institution forward the requested images for central review. The central image evaluation results will be entered into RAVE for review by the COG Operations Center and for data analysis.

The images are to be forwarded electronically to the Imaging Research Center at Children's Hospital Los Angeles via the ImageInBox.

COG institutions that are not connected via the ImageInBox can send the images on CD ROM or USB flash drive. Submitted imaging studies should be clearly marked with the COG patient ID, study number (ADV1514) and date and shipped to [name] at the address below:

8.3 Pharmacology (required)

8.3.1 Description of Studies and Assay

- ABI-009 concentrations will be determined by a validated LC/MS/MS method (AADi).
- Irinotecan and SN-38 concentrations will be determined using a validated HPLC assay with fluorescence detection ([name]/Mayo Clinic).

8.3.2 Sampling Schedule (See [Appendix XI-A](#) and [Appendix XI-B](#))

Whole blood samples (2 ml) will be obtained prior to drug administration and at the following time points:

8.3.2.1 ABI-009 Sampling Schedule during Cycle 1 (Single Agent) and Cycle 2 (Combination Therapy):

- Day 1: Pre-dose, end of infusion, and then 1, 2, 4, and 8 hrs after beginning of infusion.
- Day 2: 24 hours post-Day 1 ABI-009 dose.
- Day 4 (\pm 1 day): 72 hours (\pm 24 hours) post- Day 1 ABI-009 dose
- Day 8: Pre-ABI-009 dose.

8.3.2.2 Irinotecan/SN-38 Sampling Schedule during Cycle 2 (Combination Therapy):

- Day 1: Pre-dose, and then 10 min, 1 hr, 3 hrs, and 6 hrs post-irinotecan dose.
- Day 2: Pre-Day 2 irinotecan dose (24 hours after Day 1 irinotecan dose).

8.3.3 Sample Collection and Handling Instructions

8.3.3.1 ABI-009

Blood samples (2 ml) will be collected in EDTA tubes at a site distant from the infusion for pharmacokinetic evaluation. Samples cannot be drawn from the 2nd lumen of a multi-lumen catheter through which drug is being administered. Record the exact time that the sample is drawn along with the exact time that the infusion is started and stopped.

If the duration of infusion is changed, the sample should be collected immediately before termination of the infusion.

8.3.3.2 Irinotecan

Blood samples (2 ml) will be collected in heparinized tubes at a site distant from the infusion for pharmacokinetic evaluation. Samples cannot be drawn from the 2nd lumen of a multi-lumen catheter through which drug is being administered. Record the exact time that the sample is drawn along with the exact time that the drug is administered.

8.3.4 Sample Processing

8.3.4.1 ABI-009

- After drawing blood into EDTA tubes, gently mix by inversion 8-10 times.
- Keep on wet ice until frozen; freeze as soon as possible.
- Samples can be placed on dry ice for short-term storage; however, must be placed in the appropriate freezer within 24 hours of the draw-time (storage in -80 °C is preferred; storage at -20 °C for no more than 60 days is acceptable).

8.3.4.2 Irinotecan

Blood collected into sodium heparin tubes should be gently mixed by immediately inverting the tubes. Blood samples will then be centrifuged immediately for 15 minutes in a refrigerated centrifuge set at 805 g. Next, remove the plasma using a transfer pipette and transfer the plasma into two separate 3.5 mL polypropylene tubes. Next, immediately freeze the tubes at -80 °C and store until delivery to the Mayo Clinic (see [Section 8.3.6](#) for shipping instructions).

8.3.5 Sample Labeling

Each tube must be labeled with the patient's study registration number, the study I.D., and the date and exact time the sample was drawn. Data should be recorded on the Pharmacokinetic Study Form, which must accompany the sample(s).

8.3.6 Sample Shipping Instructions

8.3.6.1 ABI-009

Samples should be batched per patient and shipped frozen on dry ice in opaque containers at the end of Cycle 2.

Samples should be shipped using FedEx priority overnight to:

[figure not shown]
AIT Bioscience
Attn: Sample Receipt
[name]
[name]

On the day of each shipment, notify [contact] of the pending shipment, including tracking information.

8.3.6.2 Irinotecan

Samples will be held until all samples have been obtained and then sent as a single batch. Batched samples should be sent frozen on dry ice by FedEx priority overnight to:

A copy of the irinotecan pharmacokinetics specimen transmittal form should accompany the shipment and another copy should be faxed to [contact]. Samples should only be shipped on a Monday-Thursday to allow for weekday delivery. Avoid holiday shipments. Email () with the tracking number at the time of sample shipment.

8.4 Tissue Studies (required)

The key objective of the tumor molecular profiling is to identify specific markers related to the mTOR pathway that may be predictive of response to ABI-009.

Archival tumor tissue (or unstained tissue slides) should be submitted for all patients. If a patient does not have tissue available, the study chair must be notified prior to enrollment.

8.4.1 Description of Studies

8.4.1.1 Study of S6K1

Tumor tissue will be analyzed by immunohistochemistry. Antibody to be used for pS6(S235) is obtained from Cell Signaling, Catalog #2211S.

8.4.1.2 Study of 4E-BP1

Tumor tissue will be analyzed by immunohistochemistry. Antibody to be used for p4EBP1 is obtained from Cell Signaling, Catalog #2855S.

8.4.2 Sample Collection, Handling, and Shipment

Paraffin-embedded tissue blocks or slides will be shipped to the Histopathology Core of the Brigham and Women's Hospital. If sending tissue slides, it is preferred that 8-10 unstained slides (minimum: 6) are being sent. Detailed instructions regarding collection, handling, and shipping of tissue samples are located in the Tissue Study Form ([Appendix XII](#)).

8.4.2.1 Tumor Block Instructions

- Paraffin-embedded tumor specimens must be packaged appropriately and shipped at room temperature in the tumor block bags provided.
- Ensure that the specimen is labeled with the subject ID, both on the block and on the block bag.

8.4.2.2 Tumor Slides Instructions

- Cut 8-10 (minimum: 6) tissue sections 4-5 microns thick and mount on positively charged slides.
- Number sequentially; write the subject ID and original block ID on frosted end of slide.
- Place the slides in the pre-labeled slide holders provided and write the subject ID on the label.

All samples must be shipped under ambient conditions, Monday – Thursday ONLY with a corresponding pathology report containing the subject ID and the block ID. Ensure to de-identify the pathology report.

Before shipping, a “Work Request for Processing, Sectioning & Staining” and a “Work Request for Standardized Immunohistochemistry Services” must be submitted online at <http://pathcore.hms.harvard.edu>. Please follow the instructions posted on the protocol page of the COG website.

Samples should be shipped to:

Specialized Histopathology Core
Brigham and Women’s Hospital
[name]
[name]
[name]

Please contact [contact] or the COG study-specific research coordinator with protocol or work order related questions.

8.4.3 Sample Labeling

Each sample must be labeled with the patient’s study registration number, the study I.D., and the date and time the sample was taken. Data should be recorded on the Tissue Study Form, which must accompany the sample(s).

9.0 AGENT INFORMATION

█ [REDACTED]

█ [REDACTED]

[REDACTED]

[REDACTED]

[REDACTED]

[REDACTED]

[REDACTED]

[REDACTED]

[REDACTED]

[REDACTED]

[REDACTED]

[REDACTED]

[REDACTED]

[REDACTED]

[REDACTED]

[REDACTED]

[REDACTED]

[REDACTED]

[REDACTED]

[REDACTED]

[REDACTED]

[REDACTED]

[REDACTED]

[REDACTED]

[REDACTED]

[REDACTED]

[REDACTED]

[REDACTED]	[REDACTED]
[REDACTED]	[REDACTED]
[REDACTED]	[REDACTED]
[REDACTED]	[REDACTED]

	
■ [REDACTED]■ [REDACTED]■ [REDACTED]■ [REDACTED]■ [REDACTED]■ [REDACTED]■ [REDACTED]■ [REDACTED]
[REDACTED]	[REDACTED]

[REDACTED]

■ [REDACTED]

[REDACTED]

[REDACTED]

■ [REDACTED]

[REDACTED]

[REDACTED]

[REDACTED]

[REDACTED]

[REDACTED]

9.2 **CEFIXIME**
(Suprax®) NSC# NA

(11/17/17)

9.2.1 Source and Pharmacology

Cefixime is a third generation cephalosporin antibiotic for oral administration that inhibits bacterial cell wall synthesis by binding to one or more of the penicillin-binding proteins and interfering with the final transpeptidation step of peptidoglycan synthesis. Its spectrum of activity is similar to other third-generation agents, including Enterobacteriaceae, and β -lactamase producing *H. influenzae* and *N. gonorrhoeae*, and *Staph. aureus*. When taken orally, it is about 40%-50% absorbed whether administered with or without food. The area under the time versus concentration curve is greater by approximately 10%-25% with the oral suspension than with the tablet after doses of 100 to 400 mg, when tested in normal *adult* volunteers. This increased absorption should be taken into consideration if the oral suspension is to be substituted for the tablet. Cefixime serum half-life is approximately 3-4 hours. It is excreted primarily by the kidney. There is no evidence of metabolism of cefixime *in vivo*.

9.2.2 Toxicity

Incidence	Toxicities
Common (>20% of patients)	None known
Occasional (4-20% of patients)	Diarrhea, nausea, flatulence, loose or frequent stools

Incidence	Toxicities

Rare ($\leq 3\%$ of patients)
	
Erythema multiforme, pruritus, rash maculo-papular, Stevens-Johnson syndrome, toxic epidermal necrolysis, urticaria, angioedema, abdominal pain, pseudomembranous colitis, dyspepsia; transient white blood cell decrease, neutrophil count decreased, platelet count decreased; transient jaundice, alanine aminotransferase increased, aspartate aminotransferase increased, bilirubin increased; anaphylaxis, allergic reaction; dizziness, headache, seizure, acute kidney injury, creatinine increased, vaginal infection, vomiting.

Pregnancy & Lactation
	
Pregnancy Category B
 
Teratogenic effects were not observed in animal reproduction studies. Cefixime crosses the placenta and can be detected in the amniotic fluid. There are no well-controlled studies of cefixime in pregnant women; effects of cefixime on the fetus are unknown. An increase in most types of birth defects was not found following first trimester exposure to cephalosporins. It is not known whether cefixime is excreted in human milk.

9.2.3 Formulation and Stability

Cefixime is available in scored 400 mg film coated tablets, 400 mg capsules, 100 mg chewable tablets, and 200 mg chewable tablets. The chewable tablets are tutti-frutti flavor and contain aspartame and fd&c red #40 aluminum lake. Cefixime is also available in two strengths as a powder for oral suspension, which when reconstituted, provides either a 100 mg/5mL or 200 mg/5 mL suspension. The powder for oral suspension is strawberry flavored and contains sodium benzoate, sucrose, and xanthan gum. After reconstitution, suspension may be stored for 14 days at room temperature or under refrigeration.

Cefixime tablets and powder for oral suspension are stored at 20 - 25°C (68 - 77°F). Do not freeze. The suspension bottle should be kept tightly closed.

9.2.4 Guidelines for Administration

See Treatment and Dose Modification sections of the protocol.

Cefixime may be administered with or without food. Administration with food may decrease abdominal distress. Shake the suspension prior to withdrawing dose or administration.

9.2.5 Supplier

Commercially available from various manufacturers. See package insert for further information

9.3 IRINOTECAN

[CPT-11, Camptothecin-11,7-ethyl-10-(4-[1-piperidino]-1-piperidino)-carbonyloxy-camptothecin), Camptosar®], NSC #616348 (03/07/17)

9.3.1 Source and Pharmacology

Irinotecan is a semisynthetic water-soluble analog of camptothecin (a plant alkaloid isolated from *Camptotheca acuminata*). Irinotecan is a prodrug that requires conversion, by the carboxylesterase enzyme to the topoisomerase-I inhibitor, SN-38 in order to exert anti-tumor activity. SN-38 is approximately 1000 times more potent than irinotecan. Camptothecins interact specifically with the enzyme topoisomerase I which relieves torsional strain in DNA by inducing reversible single-strand breaks. Irinotecan and its active metabolite SN-38 bind to the topoisomerase I-DNA complex and prevent religation of these single-strand breaks. Current research suggests that the cytotoxicity of irinotecan is due to double-strand DNA damage produced during DNA synthesis when replication enzymes interact with the ternary complex formed by topoisomerase I, DNA, and either irinotecan or SN-38. Renal excretion is a minor route of elimination of irinotecan. The majority of the drug is metabolized in the liver. SN-38 is conjugated to glucuronic acid and this metabolite has no anti-tumor activity. The extent of conversion of SN-38 to its glucuronide has been inversely correlated with the risk of severe diarrhea, because the other major route of SN-38 excretion is biliary excretion by canalicular multispecific organic anion transporter (cMOAT) which presumably leads to mucosal injury. In addition, APC and NPC are oxidative metabolites of irinotecan dependent on the CYP3A4 isoenzyme. After intravenous infusion of irinotecan in humans, irinotecan plasma concentrations decline in a multiexponential manner, with a mean terminal elimination half-life of about 6 to 12 hours. The mean terminal elimination half-life of the active metabolite SN-38 is about 10 to 20 hours. Irinotecan is 30% to 68% bound to albumin and SN-38 is approximately 95% bound to albumin.

9.3.2 Toxicity

Incidence	Toxicities

Common (> 20% of patients)
	
 • Anemia • Thrombocytopenia • Neutrophil count decreased • White blood cell count decreased • Nausea • Vomiting • Constipation • Anorexia • Fever • Asthenia • Cholinergic symptoms: (rhinitis, increased salivation, miosis, lacrimation, diaphoresis, flushing, and intestinal hyperperistalsis that can cause abdominal cramping and diarrhea) • Alopecia • Bilirubin increased • Mucositis • Dyspnea • Cough • Weight loss • Pain

Occasional (4-20% of patients)
	
 • Abdominal fullness • Flatulence • Vasodilation • Hypotension • Dehydration • Edema • AST increased • Alkaline phosphatase increased • Ascites • Jaundice • Febrile neutropenia • Infection • Headache • Dizziness • Chills • Insomnia • Rash • Dyspepsia • Somnolence • Thromboembolic events • Pneumonia

Rare (≤ 3% of patients)
	
 • Anaphylaxis • Bradycardia • Disorientation/confusion • Colitis • Renal failure (secondary to severe dehydration)

	
 • Ileus • Pancreatitis • Pneumonitis (L)
Pregnancy & Lactation	Fetal toxicities and teratogenic effects of irinotecan have been noted in animals at doses similar or less than those used in humans. Toxicities include: decreased skeletal ossification, multiple anomalies, low birth weight and increased fetal mortality. It is not known if irinotecan is excreted into breast milk but it is excreted into rat milk.

(L) Toxicity may also occur later

9.3.3 Formulation & Stability

Each mL of irinotecan injection contains 20 mg irinotecan (on the basis of the trihydrate salt), 45 mg sorbitol, and 0.9 mg lactic acid. When necessary, pH has been adjusted to 3.5 (range, 3.0 to 3.8) with sodium hydroxide or hydrochloric acid. Irinotecan is available in single-dose amber glass vials in 40 mg (2 mL), 100 mg (5 mL), 300 mg (15 mL), and 500 mg (25 mL). Store at controlled room temperature 15°-30°C (59°-86°F). Protect from light. It is recommended that the vial (and backing/plastic blister) should remain in the carton until the time of use.

9.3.4 Guidelines for Administration

See Treatment and Dose Modifications sections of the protocol.

For oral use, the appropriate volume of irinotecan solution (20 mg/ml) is drawn up undiluted into a plastic oral syringe. Each dose is to be mixed with juice (cranberry, cranapple, cranberry, or other “cran” juice or juice cocktail) **immediately** before administration. The oral syringes containing undiluted irinotecan are stable for 21 days when stored in a refrigerator. Irinotecan has a very unpleasant flavor, therefore, the juice will be used to mask the drug taste (See [Appendix VI](#)). See protocol for pre-medication and supportive care measures.

9.3.5 Supplier

Commercially available from various manufacturers. See package insert for more detailed information.

9.4 **TEMOZOLOMIDE - ORAL** (Temodar[®], Temodal[®]) NSC #362856

(06/26/18)

9.4.1 Source and Pharmacology:

An orally administered alkylating agent, a second generation imidazotetrazine. A prodrug of MTIC, temozolomide spontaneously decomposes to MTIC at physiologic pH. Exerts its effect by cross-linking DNA. This is likely a site-specific alkylation at the O⁶-position of guanine with some effect at the N⁷-position. Temozolomide reaches its peak concentration in 1 hour. Food reduces the rate and extent of absorption. It has an elimination half-life of 1.13 hr (intraperitoneally) and 1.29 hr (orally) with an oral bioavailability of 0.98. Total apparent body clearance is 100 mL/min/m² and plasma elimination half-life is ~ 100 minutes.

9.4.2 Toxicity

The table below lists the anticipated toxicity profile of temozolomide (oral):

Incidence	Toxicities
Common (>20% of patients)	Constipation, nausea, vomiting, diarrhea, anorexia, alopecia, alanine aminotransferase increased, aspartate aminotransferase increased, ataxia, anxiety, depression, insomnia, nervous system disorders – other: hemiparesis or paresis, dizziness, gait disturbance, amnesia, paresthesia, somnolence, headache, seizure, fatigue
Occasional (4-20% of patients)	Edema limbs, localized edema, rash maculopapular, dysphagia, mucositis oral, anemia, platelet count decreased, white blood cell count decreased, lymphocyte count decreased, aplastic anemia, blood bilirubin increased, urinary frequency, cough, upper respiratory infection, sinusitis
Rare (≤ 3% of patients)	Stevens-Johnson syndrome, toxic epidermal necrolysis, erythema multiforme, hypercalcemia, lower gastrointestinal hemorrhage, upper gastrointestinal hemorrhage, cholecystitis, alkaline phosphatase increased, myelodysplastic syndrome, leukemia secondary to oncology chemotherapy, infections and infestations – other: Pneumocystis pneumonia, pulmonary fibrosis, anaphylaxis, allergic reaction, hepatic failure
Pregnancy & Lactation	Pregnancy Category D Adequate, well-controlled studies have not been conducted in humans. Women of childbearing potential should be advised against becoming pregnant while taking temozolomide and for at least 6 months following the end of therapy. Temozolomide administration to rats and rabbits at 3/8 and 3/4 the human dose resulted in the development of malformations of the external organs, soft tissues, and skeleton. These animal studies also demonstrated embryoletality (increased resorptions) at similar doses. There is no information available regarding the transmission of temozolomide during lactation; women should avoid breastfeeding while receiving temozolomide.

9.4.3 Formulation and Stability

Temozolomide capsules are available in six different strengths (5, 20, 100, 140, 180, 250 mg). The capsules vary in size, color, and imprint according to strength. In the US, capsules are packaged in 5-count and 14-count bottles. In other countries temozolomide may be packaged in 5-count, 14-count or 20-count bottles. Temozolomide capsules are stored at controlled room temperature.

9.4.4 Guidelines for Administration

See Treatment and Dose Modification sections of the protocol.

There is a potential for medication errors involving temozolomide capsules resulting in drug overdosages, which may have been caused by dispensing/taking the wrong number of capsules per day and/or product usage exceeding the prescribed dosing schedule.

When dispensing, it is extremely important that prescribing and dispensing include clear instructions on which capsules, and how many of each capsule(s) are to be taken per day. Only dispense what is needed for the course, and clearly indicate how many days of dosing the patient will have and how many days are without temozolomide dosing. When counseling patients, it is important for each patient/parent to understand the number of capsules per day and the number of days that they take temozolomide. It is also important for the patient/parent to understand the number of days that they will be off the medication.

Each strength of temozolomide must be dispensed in a separate vial or in its original container (e.g., bottle or sachet). Based on the dose prescribed, determine the number of each strength of temozolomide capsules needed for the full course as prescribed by the physician. For example, 275 mg/day for 5 days would be dispensed as five 250 mg capsules, five 20 mg capsules, and five 5 mg capsules. Label each container with the appropriate number of capsules to be taken each day. Dispense to the patient/parent, making sure each container lists the strength (mg) per capsule and that he or she understands to take the appropriate number of capsules of temozolomide from each bottle or vial to equal the total daily dose prescribed by the physician. Institutions that have the capability to dispense temozolomide as daily doses in a blister pack may do so, taking specific precautions to ensure that the appropriate dose is provided and that the patient is educated to understand the daily dosing regimen.

For children unable to swallow the capsules whole, the oral capsules may be formulated into a suspension. To prepare a 10 mg/mL suspension triturate the contents of ten 100 mg capsules (1000 mg), 500 mg povidone K-30 and 25 mg anhydrous citric acid dissolved in 1.5 mL purified water in a glass mortar to form a uniform paste. To the paste add 50 mL of Ora-Plus[®] by adding a small amount, mixing, and then adding the balance. Transfer to a glass graduated cylinder. Add Ora-Sweet[®] or Ora-Sweet[®] SF to a total volume of 100 mL by rinsing the mortar with small amounts of the syrup (Ora-Sweet[®] or Ora-Sweet[®] SF). Rinse at least four times. Package in an amber plastic prescription bottle. The packaged suspension should be stored in the refrigerator at 2°-8°C (36-46°F) for no more than 2 weeks after preparation. The suspension should be shaken well before each use. Procedures for proper handling and disposal of cytotoxic drugs should be used when preparing the suspension.³⁵

Alternatively, the capsules can be opened and mixed with apple sauce or juice, which should be used immediately after mixing or must be used in 2 hours after mixing (See [Appendix V](#)).

9.4.5 Supplier:

Commercially available. See package insert for further information.

10.0 CRITERIA FOR REMOVAL FROM PROTOCOL THERAPY AND OFF STUDY CRITERIA

10.1 Criteria for Removal from Protocol Therapy

- a) Clinical (including physical examination or serum tumor markers) or radiographic evidence of progressive disease (See [Section 12.0](#)).

- b) Adverse Events requiring removal from protocol therapy (See [Section 6.0](#)).
- c) Refusal of protocol therapy by patient/parent/guardian
- d) Non-compliance that in the opinion of the investigator does not allow for ongoing participation.
- e) Completion of 35 cycles of therapy.
- f) Physician determines it is not in the patient's best interest.
- g) Repeated eligibility laboratory studies (CBC with differential, bilirubin, ALT (SGPT) or serum creatinine) are outside the parameters required for eligibility prior to the start of ABI-009 (See [Section 8.1](#)).
- h) Study is terminated by Sponsor.
- i) Pregnancy

Patients who are removed from protocol therapy during cycle 1 should continue to have the required observations in [Section 8.1](#) until the originally planned end of the cycle or until all adverse events have resolved per [Section 13.4.4](#), whichever happens LATER. The only exception is with documentation of the patient's withdrawal of consent. Patients who are removed from protocol therapy in subsequent cycles should have the necessary observations to ensure adequate clinical care.

Patients who are off protocol therapy are to be followed until they meet the criteria for Off Study (see below). Ongoing adverse events, or adverse events that emerge after the patient is removed from protocol therapy, but within 30 days of the last dose of investigational agent, must be followed and reported via RAVE and CTEP-AERS (if applicable). Follow-up data will be required unless consent is withdrawn.

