2.4.1 Prior Experience in Children

There have been no pediatric studies of ABI-009.

2.5 **Overview of Proposed Pediatric Study**

We propose to conduct a Phase 1 study of ABI-009 in children with relapsed/refractory solid tumors using the rolling 6 design. Cycle 1 will aim to establish tolerability and safety and to

obtain pharmacokinetics of ABI-009 as a single agent dosed on days 1 and 8 of a 21-day cycle. Additionally, Cycle 2+ will aim to determine the MTD and/or RP2D of ABI-009 in combination with temozolomide and irinotecan. The ABI-009 starting dose will be 35 mg/m² as a single agent during Cycle 1, while Cycle 2+ dosing and scheduling in combination with irinotecan (90 mg/m²) and temozolomide (125 mg/m²) will mimic the Phase 1 pediatric trial ADVL0918.²³

2.6 Rationale for Amendment #4 (Addition of Dose Level -2 and modification of the definition of hematological DLT)

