5.5 Definition of Dose-Limiting Toxicity (DLT)

DLT will be defined as any of the following events that are possibly, probably or definitely attributable to protocol therapy. The DLT observation period for the purposes of dose-escalation will be Cycles 1 and 2 of therapy.

Dose limiting hematological and non-hematological toxicities are defined differently.

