Because rapamycin is a substrate for both CYP3A4 and P-gp, concomitant administration with inhibitors or inducers of CYP3A4 and P-gp may alter the pharmacokinetics of ABI-009. Inhibitors of CYP3A4 may decrease the metabolism of rapamycin and increase rapamycin concentrations, while inducers of CYP3A4 may increase the metabolism of rapamycin and decrease rapamycin concentrations. Drugs that may increase rapamycin blood concentrations include antifungal agents (e.g., voriconazole, itraconazole, posaconazole), macrolide antibiotics (e.g., clarithromycin, telithromycin), and other drugs (e.g., HIV-protease inhibitors). Drugs that may decrease rapamycin concentrations include anticonvulsants (e.g., carbamazepine, phenobarbital, phenytoin), and antibiotics (e.g., rifabutin, rifampin). See [Appendix XIV](#) for more information on CYP3A4 inducers and inhibitors.

8.0 **EVALUATIONS/MATERIAL AND DATA TO BE ACCESSIONED**

8.1 **Required Clinical, Laboratory and Disease Evaluation**

All clinical and laboratory studies to determine eligibility must be performed within 7 days prior to enrollment unless otherwise indicated. Laboratory values used to assess eligibility (see [Section 4.0](#)) must be no older than seven (7) days at the start of therapy. Laboratory tests need **not** be repeated if therapy starts **within** seven (7) days of obtaining labs to assess eligibility. If a post-enrollment lab value is outside the limits of eligibility, or laboratory values are older than 7 days, then the following laboratory evaluations must be re-checked within 48 hours prior to initiating therapy: CBC with differential, bilirubin, ALT (SGPT) and serum creatinine. If the recheck is outside the limits of eligibility, the patient may not receive protocol therapy and will be considered off protocol therapy. Imaging studies must be obtained within 14 days prior to start of protocol therapy (repeat the tumor imaging if necessary).

STUDIES TO BE OBTAINED	Pre-Study	Cycles 1 & 2	Prior to Subsequent Cycles [^]
History	X	Weekly	X
Physical Exam with vital signs	X	Weekly	X
Height, weight, BSA	X	Prior to Cycle 2	X
Performance Status	X	Prior to Cycle 2	X
CBC, differential, platelets	X	Twice Weekly (every 3 to 4 days) ³	Weekly ⁴
Pharmacokinetics ¹	X	X	
Urinalysis	X		
Electrolytes including Ca ⁺⁺ , PO ₄ ³⁻ , Mg ⁺⁺ , glucose ¹¹	X	Weekly	X
Creatinine, ALT, bilirubin	X	Weekly	X
Albumin	X	Prior to Cycle 2	X
INR	X		
Total Cholesterol, Triglycerides ¹⁰	X	Weekly	X

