11.2.2 Maximum Tolerated Dose

- The MTD will be the maximum dose at which fewer than one-third of patients experience a DLT (See [Section 5.5](#)) during Cycles 1 and 2 of therapy.
- In the unlikely event that two DLTs observed out of 6 evaluable patients are different classes of Adverse Effects (e.g. hepatotoxicity and myelosuppression), AND all of the following conditions are met, expansion of the cohort to 12 patients will be considered:
 - One of the DLTs does not appear to be dose-related
 - The Adverse Effects are readily reversible
 - The study chair, DVL statistician, DVL committee chair or vice chair, and IND sponsor all agree that expansion of the cohort is acceptable

If fewer than 1/3 of patients in the expanded cohort experience dose-limiting toxicities, the dose escalation can proceed.

- The DLTs observed in the pharmacokinetic (PK) expansion cohort will be counted towards the total number of DLTs observed at the MTD during the dose escalation portion of the study. If $\geq 1/3$ of the cohort of patients at the MTD (during the dose escalation plus the PK expansion) experience DLT then the MTD will be exceeded.

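### Section 10.1 keeps the scheduled safety tests after removal from therapy only for Cycle 1, although the DLT window runs through Cycle 2

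*Combined protocol and SAP*

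**What the plan says.** **The window.** Section 5.5 states: "The DLT observation period for the purposes of dose-escalation will be Cycles 1 and 2 of therapy". Section 11.2.2 uses the same two cycles: "The MTD will be the maximum dose at which fewer than one-third of patients experience a DLT", counted over Cycles 1 and 2.

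**The monitoring.** The Section 8.1 table has a single column for Cycles 1 and 2, with blood counts twice a week and chemistry and lipids weekly. The next column, "Prior to Subsequent Cycles", therefore starts at Cycle 3. Footnote 3 asks for counts at least every 2 to 3 days once Grade 4 neutropenia is present, until it recovers to Grade 3 or meets the DLT criteria.

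**Evaluability.** Section 11.2.1 requires 85% of the prescribed dose in each of the two cycles and the appropriate toxicity monitoring studies. A patient who has no DLT and is not evaluable is replaced.

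**After removal.** Section 10.1 has two rules. For the first cycle: "Patients who are removed from protocol therapy during cycle 1 should continue to have the required observations", until the planned end of the cycle or resolution of adverse events, whichever is later. For the rest: "Patients who are removed from protocol therapy in subsequent cycles should have the necessary observations to ensure adequate clinical care". It also requires follow-up and reporting of ongoing events and of "adverse events that emerge after the patient is removed from protocol therapy, but within 30 days of the last dose of investigational agent".

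**The concern.** Section 10.1 divides the cycles after Cycle 1; Sections 5.5, 8.1, 11.2.1 and 11.2.2 divide them after Cycle 2. Cycle 2 is thus inside the DLT window but outside the rule that keeps the scheduled tests going after removal.

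Cycle 2 matters most for the primary aim. Cycle 1 is single-agent ABI-009, and Section 2.5 says "Cycle 2+ will aim to determine the MTD and/or RP2D of ABI-009 in combination with temozolomide and irinotecan". All DLTs so far were hematologic, and the four described in Section 2.6 were platelet count decreases, which are found only by blood counts. Several hematologic DLTs in Section 5.5.2 are defined by duration (about 7 days), so serial counts are needed to establish them.

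At Dose Level -2 one patient decides the outcome: at most 1 of 6 with a DLT leads to the PK expansion, and 2 or more closes the study (Section 11.3.1). Removal during Cycle 2 is foreseeable, because footnote 12 of Section 8.1 lets a patient who progresses in Cycle 1 go on to Cycle 2 if the other conditions are met.

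**Working it through.** **1. The sections side by side**

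| Section | Subject | Cycles grouped together |
|---|---|---|
| 5.5, 11.2.2 | DLT window, MTD | 1 and 2 |
| 8.1 | Test schedule | 1 and 2, then 3 onward |
| 11.2.1 | Dose and monitoring for evaluability | 1 and 2 |
| 10.1 | Scheduled tests after removal | 1 only, then 2 onward |

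**2. Does the 30-day adverse-event rule close the gap?** Thirty days after a Cycle 2 Day 1 dose is Day 31, and after a Day 8 dose Day 38. Both lie beyond Day 21, so the reporting period spans the rest of the cycle. But it requires no tests. A cytopenia already present at removal is an ongoing event and must be followed (Sections 10.1 and 13.4). A new asymptomatic one is reported only if someone happens to test for it.

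**3. What is not required after a Cycle 2 removal.** Calendar assumed from the Section 8.1 frequencies: counts on Days 1, 4, 8, 11, 15 and 18; chemistry on Days 1, 8 and 15.
- Removal after the Day 8 dose: 21 - 8 = 13 days, 3 counts (Days 11, 15, 18) and 1 panel (Day 15).
- Removal after Day 1: 21 - 1 = 20 days, 5 counts and 2 panels.

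Thirteen days is long enough for a 7-day cytopenia to begin and meet its duration criterion unobserved.

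**4. Who can be lost avoidably.** Planned Cycle 2 doses are 5 temozolomide + 5 irinotecan + 2 ABI-009 = 12.
- After the Day 8 dose, with none held: 12/12 = 100%. The 85% rule is met, and monitoring is the only Cycle 2 condition left.
- Before the Day 8 dose: ABI-009 is 1/2 = 50%, which fails 85% if the rule applies per agent. Tests then serve only to detect a DLT. If doses are pooled by count, completing Day 5 gives 11/12 = 92%, which passes. Section 11.2.1 does not say which applies.

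**5. The plan's enrolment figures, reproduced.** N/(1 - d) with d = 0.30 (Section 11.1.1): 12/0.70 = 17.1, so 18; 18/0.70 = 25.7, so 26. With the 18 already enrolled, the totals are 36 and 44. All match the plan.

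**6. Cost of losing one evaluable patient.** 1/0.70 = 1.43 enrolments. Eighteen patients in 9 to 18 months is 1 to 2 per month, so 1.43 enrolments take 0.7 to 1.4 months. The replacement's own DLT window adds up to 2 × 21 = 42 days.

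**7. Illustration with an assumed loss q (no figure is given).** Extra enrolments for 12 evaluable patients = 12/(1 - q) - 12.

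| q | Extra enrolments |
|---|---|
| 2% | 0.24 |
| 5% | 0.63 |
| 10% | 1.33 |

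These may already lie within the 30% allowance.

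**8. Direction of bias.** If patients are dropped without regard to DLT status, with loss fraction m, the observed rate is p(1 - m)/[p(1 - m) + (1 - p)(1 - m)] = p. At p = 1/3, the chance of at most 1 DLT in 6 stays (2/3)^6 + 6(1/3)(2/3)^5 = 256/729 = 0.351 for any m. A shift needs a link between removal or missing tests and DLT status, or a missed DLT kept in the count as DLT-free. The documents do not allow either to be quantified.

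**The case against.** The strongest reply is that the gap is narrow and partly covered elsewhere. Adverse events are followed for 30 days, suspected DLTs must be reported within 24 hours (Section 5.4), leadership reviews evaluability and DLTs weekly (Section 14.4.2), and Section 11.2.1 independently makes monitoring a condition of evaluability. Patients removed because of a DLT are already counted, and scheduled imaging falls at the end of Cycle 2, which limits earlier removals for progression. Nothing in the documents shows that a DLT was missed this way, and the 7 of 13 inevaluable patients at Dose Level -1 are reported without reasons.

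The narrowness stands. The cover does not close the gap, because each safeguard acts on an event already detected and none requires a blood test.

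It is also fair that one patient cannot suffer both harms. If clinical-care observations are not judged appropriate monitoring, a patient without a documented DLT is replaced. If they are, the patient stays, counted as DLT-free with part of the window not observed on schedule. Section 11.2.1 does not say which applies, and either result is worse than scheduled tests.

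Some figures are soft. Counting every 3 days after Day 8 (Days 11, 14, 17, 20) gives 4 counts, not 3. The 42 days are an upper limit, because rolling enrolment lets observation periods overlap.

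**Conclusion.** The concern holds. As written, Section 10.1 leaves part of the combination-therapy DLT window without required tests after a Cycle 2 removal, in conflict with Sections 5.5, 8.1, 11.2.1 and 11.2.2. The consequence is incomplete ascertainment of new asymptomatic or duration-defined laboratory DLTs and avoidable loss of evaluable patients, clearest after the Day 8 dose.

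The text mismatch is certain; the size of its effect is not. The number affected is unknown and probably small, and the inevaluable patients at Dose Level -1 cannot be attributed to it. The cost per lost patient rests on the plan's 30% inevaluability and 1 to 2 enrolments per month; the test counts rest on the assumed calendar. No direction of bias in the DLT rate is claimed, and the planned totals of 36 and 44 are not in question. It should be fixed because one patient decides the outcome at Dose Level -2 and the repair is small.

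**What to change.** Reconcile Section 10.1 with Sections 5.5, 8.1 and 11.2.1 by two substitutions:
- for the rule that keeps the Section 8.1 observations, replace *during cycle 1* with *during Cycle 1 or Cycle 2 (the DLT observation period)*;
- for the clinical-care rule, replace *in subsequent cycles* with *in Cycle 3 or later*.

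The cost is a short wording amendment and, for the few patients removed in Cycle 2, tests already on the schedule: 13 days after a Day 8 removal, about 20 days at most, or longer if adverse events are unresolved under the existing later-of rule. Taken literally this also brings the weekly history, examination, lipids and oxygen saturation and the end-of-Cycle-2 tumor evaluation. The sponsor could limit the extension to the toxicity observations, and should check the later-of rule against the 30-day off-study point in Section 10.2. Patients who withdraw consent, or who go off study by joining another COG therapeutic trial, would remain uncovered. No dose, treatment rule or sample-size figure changes.
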